
Objectives:
 
It is hypothesised that triptorelin pamoate PR 3-month will offer non-inferior efficacy to triptorelin acetate PR 1-month in the treatment of Chinese subjects with endometriosis (as previously demonstrated in a European population in Study E-28-52014-705).
 
Primary objective:
 
 To assess the efficacy of triptorelin pamoate PR 3-month formulation in Chinese female subjects with endometriosis by demonstrating the noninferiority of triptorelin pamoate PR 3-month formulation injected once as compared to triptorelin acetate PR 1-month formulation injected 3 times consecutively, assessed by the percentage of subjects castrated (oestradiol (E_2) ≤ 184 pmol/L or 50 pg/mL) at Week 12. 
Secondary objectives:
 
 To assess other efficacy parameters including the percentage of subjects castrated at other time points, E_2, luteinising hormone (LH) and follicle stimulating hormone (FSH) concentrations, and the impact on endometriosis-associated pelvic pain. To assess the safety profile of triptorelin pamoate PR 3-month. To assess the pharmacokinetics (PK) of triptorelin pamoate PR 3-month and compare to triptorelin acetate PR 1-month. 
Exploratory objectives:
 
 To assess efficacy parameters (percentage of subjects castrated, E_2, LH and FSH concentrations and impact on endometriosis-associated pelvic pain) after Week 12. To explore the PK/pharmacodynamics (PD) of triptorelin pamoate PR 3-month in a subset of subjects (PD markers being E_2, FSH and LH). 	

Methodology:
 
This prospective, multicentre, randomised, open-label, parallel-group, active-controlled study will compare triptorelin pamoate PR 3-month with triptorelin acetate PR 1-month in the treatment of endometriosis in Chinese subjects.
 
Subjects with endometriosis will be recruited and screened for eligibility up to 5 weeks prior to the first dose of investigational medicinal product (IMP), which must occur during the follicular phase of the menstrual cycle. Eligible subjects will be stratified by endometriotic surgical history and endometriosis-associated pelvic pain (assessed by a visual analogue scale (VAS)) and randomised in a 1:1 ratio to receive either triptorelin pamoate PR 3-month once per 12 weeks or triptorelin acetate PR 1-month once per 4 weeks for a 24-week treatment phase. All subjects will visit the study site every 4 weeks until Week 24, with the exception of the subgroup participating in the full PK and exploratory PD evaluations (up to 32 subjects, including up to 16 from each treatment group; to be enrolled at
	

selected sites), who will have additional study visits during the treatment phase. If needed in the opinion of the investigator, "add back" treatment (recommended as, but not limited to, tibolone at a dose of 2.5 mg once daily) may be applied from Week 12. After 24 weeks' study treatment, subjects will be followed up by telephone every 4 weeks until menses recovery or Week 40 (whichever is earlier), except for subjects receiving triptorelin pamoate PR 3-month and participating in the full PK/PD subgroup, who will visit the study site. The first visit after the menses recovery or Week 40 will be considered as the end of study visit. All subjects will attend the study site for the end of study visit.

The duration of the study is a minimum of 24 to 40 weeks, plus up to 5 weeks for the screening period.

Number of subjects planned:

300 randomised subjects (150 receiving triptorelin pamoate PR 3-month and 150 receiving triptorelin acetate PR 1-month).

Diagnosis and criteria for inclusion:

All subjects must fulfil all of the following criteria to be included in the study:

- (1) Female subjects aged from 18 to 45 years inclusive at the date of informed consent.
- (2) Provided written informed consent.
- (3) A history of active and regular menstrual cycles of 21 to 35 days (inclusive) in the 6 months prior to the screening visit.
- (4) A diagnosis of endometriosis, confirmed by laparoscopy or laparotomy within 10 years prior to the screening visit.
- (5) Requires treatment with a gonadotrophin releasing hormone (GnRH) agonist for a period of 6 months in the judgement of the investigator.
- (6) A negative pregnancy test prior to the start of treatment.
- (7) Not at risk of pregnancy, i.e. subjects of childbearing potential must be actively using barrier contraception throughout the study treatment until menses resume.

Subjects will be excluded from the study if any of the following apply:

- (1) Subject is menopausal.
- (2) Subject is pregnant or lactating.
- (3) A current history of undiagnosed abnormal genital bleeding.
- (4) Received treatment with a GnRH agonist within 6 months prior to the screening visit.
- (5) A history of hypersensitivity to GnRH agonists and/or any of the excipients.
- (6) Received any other hormonal treatment within 3 months prior to the screening visit (oestrogens, progestogens, danazol, gestrinone and cyproterone acetate etc).
- (7) Has been treated for endometriosis with traditional Chinese medicine within 1 month prior to screening.
- (8) It is anticipated that the subject will require surgery during the study period.
- (9) Chronic pelvic pain that is not caused by endometriosis, that would interfere with the assessment of endometriosis-associated pelvic pain.
- (10) A significant endocrine disorder (except controlled diabetes mellitus).
- (11) Known history of human immunodeficiency virus (HIV) infection.
- (12) Known history of chronic active hepatitis, including viral hepatitis carriers (hepatitis B or hepatitis C).
- (13) Clinically significant hepatic (any liver enzyme $> 2 \times$ the upper limit of normal (ULN)) or renal (creatinine $> \text{ULN}$) abnormalities or any other dysfunction according to the investigator's judgement.
- (14) Any psychiatric illness, severe or unstable known illness that in the investigator's opinion could affect the safety, conduct or outcome of the study.

- (15) Use of concomitant therapy, which in the investigator's opinion may interfere with the evaluation of study treatment efficacy and safety.
- (16) Treatment with any other experimental drug or device within 90 days prior to the screening visit and/or expectation of treatment with any other experimental drug or device during the conduct of the study.
- (17) Any malignancy except curatively-treated basal cell skin cancer.
- (18) Unable or unwilling to comply with the protocol.
- (19) A history of alcohol and/or drug abuse.
- (20) Abnormal pelvic type B ultrasonography finding that would contraindicate the use of triptorelin.

Test product, dose, mode of administration:

The test product is triptorelin pamoate PR 3-month formulation (triptorelin pamoate for injection 15 mg).

Triptorelin pamoate PR 3-month is a slightly yellow, freeze-dried cake or powder and solvent for suspension. For a single dose, the powder comprises triptorelin pamoate, D, L-lactide-coglycolide polymer, mannitol, sodium carmellose and polysorbate 80. The solvent provided for injection is a 2 mL ampoule of mannitol and water.

The product is administered by the intramuscular route only. The powder is reconstituted with the solvent provided and injected immediately after reconstitution. The product is administered as a single intramuscular injection every 12 weeks.

Duration of treatment: 24 weeks

Reference therapy, dose and mode of administration:

The comparator product is triptorelin acetate PR 1-month formulation (triptorelin acetate for injection 3.75 mg).

Triptorelin acetate PR 1-month is a practically white, freeze-dried cake or powder and solvent for suspension. For a single dose, the powder comprises triptorelin acetate, D, L-lactide-coglycolide polymer, mannitol, sodium carmellose and polysorbate 80. The solvent provided for injection is a 2 mL ampoule of mannitol and water.

This product is administered by the intramuscular route only. The powder is reconstituted with the solvent provided and injected immediately after reconstitution. The product is administered as a single intramuscular injection every 4 weeks.

Criteria for evaluation:Efficacy:

Primary endpoint and evaluation:

- Percentage of subjects castrated ($E_2 \leq 184$ pmol/L or 50 pg/mL) at Week 12. The primary endpoint will be evaluated based on centralised bioanalysis of serum samples for E_2 .

Secondary endpoints and evaluations:

- Percentage of subjects castrated ($E_2 \leq 184$ pmol/L or 50 pg/mL) at Weeks 4 and 8.
- Percentage of subjects castrated ($E_2 \leq 110$ pmol/L or 30 pg/mL) at Weeks 4, 8 and 12.
- Change in endometriosis-associated pelvic pain (by 10 cm VAS) at Weeks 4, 8 and 12 compared to baseline.
- E_2 , FSH and LH concentrations at Weeks 4, 8 and 12.
- Time to menses recovery.

Pharmacokinetic/pharmacodynamic endpoints and evaluations:

A full triptorelin PK analysis will be conducted in a subgroup of up to 16 subjects in each treatment group (the full PK/PD subgroup: up to 32 subjects in total, to be enrolled at selected sites). Sparse PK samples will be taken in all subjects (in addition to the full PK subgroup) at Day 1 (baseline), and

Weeks 4, 8, 12 and 24. Additional hormone samples (E_2 , FSH and LH) will be collected for PD assessments at Weeks 1, 2, 3 and 32 in the full PK/PD subgroup.

Noncompartmental analysis will only be performed on the PK data collected for the PK/PD subgroup to assess the PK parameters for the triptorelin pamoate PR 3-month and triptorelin acetate PR 1-month formulations. Population PK analysis (modelling) will be performed on PK data from all subjects.

Exploratory endpoints will include:

- Percentage of subjects castrated (as defined by both $E_2 \leq 184$ pmol/L (50 pg/mL) and $E_2 \leq 110$ pmol/L (30 pg/mL)) at Week 24;
- Change in endometriosis-associated pelvic pain (by 10 cm VAS) at Weeks 16, 20 and 24 and the end of study visit compared to baseline;
- Concentrations of E_2 , FSH and LH at Week 24.
- The PK/PD relationship will be explored (PD markers being E_2 , FSH and LH).

Safety:

Occurrence of adverse events (AEs) throughout the study, clinical laboratory (biochemistry, haematology and urinalysis) test results and electrocardiogram (ECG) findings at screening, Week 12 and Week 24, serum hormone (E_2 , FSH and LH) concentrations at Week 40 (for those subjects whose menses do not recover at Week 40), vital signs (blood pressure and heart rate) measurements at each visit during treatment and end of study visit, physical/pelvic examination at screening, Week 12 and Week 24, pelvic type B ultrasound at screening (or within 1 month prior to screening), Week 12 (optional) and Week 24, and urinary pregnancy test at screening and baseline.

Statistical methods:

The analysis sets for the primary and secondary efficacy endpoints will be the full analysis set (FAS) and the per protocol (PP) set. If the lower limit of the 95% confidence interval (CI) of the difference in percentage of subjects castrated ($E_2 \leq 184$ pmol/L or 50 pg/mL) at Week 12 between the triptorelin pamoate PR 3-month and triptorelin acetate PR 1-month is $>-10\%$, noninferiority of triptorelin pamoate PR 3-month will be confirmed.

For secondary endpoints relating to the percentage of subjects castrated (either $E_2 \leq 184$ pmol/L or $E_2 \leq 110$ pmol/L), the number and percentage of subjects will be presented by treatment group for each visit. The difference between the treatment groups will be calculated and displayed with the 95% CI. Raw values for serum concentrations of E_2 , FSH and LH, endometriosis-associated pelvic pain (measured by VAS) and change from baseline, will be summarised, using number of available observations (n), mean, median, standard deviation (SD), and minimum and maximum values. For time to menses recovery, Kaplan-Meier curves, median time to event and 95% CIs will be provided.

Determination of sample size

The sample size was estimated based on data from Ipsen Study E-28-52014-705. Assuming the percentage of subjects castrated at Week 12 of triptorelin acetate PR 1-month treatment is no less than 92%, a sample size of 133 subjects in each treatment group will have 85% power to demonstrate the noninferiority of triptorelin pamoate PR 3-month to the comparator, when the lower limit of the 95% CI of the difference in percentage of subjects castrated at Week 12 between the treatment groups is $>-10\%$ and with a 0.025 one-sided type I error rate.

Assuming that the dropout rate will be around 10%, a sample size of 300 randomised subjects in total is planned for this study.

TABLE OF CONTENTS

LIST OF ABBREVIATIONS.....	14
1 BACKGROUND INFORMATION	16
1.1 Introduction.....	16
1.2 Triptorelin	16
1.3 Findings from Clinical Studies	17
1.4 Clinical Trial Rationale	17
1.5 Population to be Studied	17
1.6 Compliance Statement.....	17
2 PURPOSE OF THE STUDY AND STUDY OBJECTIVES.....	19
2.1 Purpose of the Study.....	19
2.2 Study Objectives	19
3 STUDY DESIGN.....	20
3.1 General Design and Study Schema	20
3.2 Endpoints and Evaluations	21
3.2.1 Primary Efficacy Endpoint and Evaluation	21
3.2.2 Secondary Efficacy Endpoints and Evaluations.....	21
3.2.3 Pharmacokinetic/Pharmacodynamic Endpoints and Evaluations	21
3.2.4 Exploratory Efficacy Endpoints and Evaluations	21
3.2.5 Safety Endpoints and Evaluations	22
3.3 Randomisation and Blinding	22
3.4 Study Treatments and Dosage	23
3.5 Study Duration	23
3.6 Stopping Rules and Discontinuation Criteria	24
3.7 Investigational Medicinal Product Preparation Storage and Accountability	24

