1 BACKGROUND INFORMATION

1.1 Introduction

Endometriosis is a disorder experienced by approximately 7% to 10% of women. It is characterised by the presence of endometrial tissue fragments outside the uterine cavity, most commonly in the pelvic area. Endometriosis is an oestradiol (E₂) dependent disease and is relieved by the administration of antioestrogens, inhibitors of endogenous E₂ secretion, and by surgical oophorectomy or ectopic tissue surgery.

The disease may be asymptomatic, but where symptoms occur they usually consist of dysmenorrhoea, cyclical abdominal or pelvic pain, and dyspareunia. In addition, 30% to 40% of patients with endometriosis are infertile. This means that between 2% and 4% of women may be infertile due to endometriosis. Symptom intensity is not necessarily dependent upon the extent of the lesions and it is not unusual for endometriosis to be discovered in asymptomatic patients undergoing laparoscopy or laparotomy for some other reason. Since the symptomatology is also nonspecific, a diagnosis of endometriosis can only be confirmed by laparoscopy or other means that provide anatomical or histological evidence.

Treatment of endometriosis depends on a woman's symptoms, pregnancy plans, and age, as well as the extent of endometriosis. In some cases no treatment is necessary. Where treatment is required, two types are currently recommended, and these can be complementary. The first is surgery to remove the ectopic endometrial tissue. Furthermore, hormone treatment is used to suppress E₂ secretion, since E₂ stimulates the growth of endometrial tissue. The hypogonadotrophic state produced by hormonal suppressants reduces the menstrual flow and leads to apoptosis of the endometriotic lesions. The principal hormonal suppressants used are gonadotrophin releasing hormone (GnRH) agonists such as triptorelin.

The purpose of triptorelin treatment of endometriosis is symptomatic relief of the condition via suppression of E₂ production. The clinical effect is associated with reduction of E₂ levels to postmenopausal levels, and hence suppression of menses. The suppression of menses is known to reduce endometriotic deposits and improve clinical symptoms. At the present time, hormonal treatment can be used either as first-line treatment or in combination with surgery, particularly in cases of extensive endometriosis. The GnRH analogues are used either pre- or postoperatively.

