5.2.2 Procedures before Study Treatment (Baseline, Visit 2 Predose)

Subjects will be instructed to contact the study centre by telephone at the onset of their menses period to arrange their baseline visit (Visit 2, Day 1), which must occur in the follicular phase (from the first to the fifth day of menses). Administration of study treatment will be initiated at the baseline visit, following randomisation to one of the two treatment groups, as specified in Section 6.1. The following procedures will be performed at baseline on Day 1 of the study, prior to administration of study treatment:

- Urine pregnancy test
- Baseline efficacy assessments (E₂, LH and FSH concentrations; VAS)
- Samples taken for sparse PK analysis
- Vital signs
- Review of pretreatment AEs
- Prior and concomitant medications/therapies
- Date of onset of menses, current menses status
- Eligibility check (inclusion/exclusion criteria)
- Randomisation
- Allocation to the full PK/PD subgroup (selected sites only)

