5.2.4 Procedures during Follow Up Period (Visit 9 to End of Study)

The purpose of the follow up period is to monitor menses recovery. Visits 9, 10 and 11 (Weeks 28, 32 and 36) will be conducted by telephone, primarily to establish if subjects' menses have recovered. If menses recover during the follow up period, subjects should attend the study site within 15 days after the first day of menses recovery. If there is no menses recovery by Week 40, the subject should attend the study site at Week 40 (Day 281±3). The first visit after menses recovery, or Week 40 (whichever is earlier) will be considered the end of study visit (see Section 5.2.4.4).

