5.2.4.4 End of Study Visit or Early Withdrawal Visit

The end of study visit will be the first visit within 15 days after the first day of menses recovery, or at Week 40 (Day 281±3), whichever is earlier. Subjects who withdraw from the study early will also attend an end of study visit.

Subjects who participate in the study in compliance with the protocol for 24 weeks of study drug administration will be considered to have completed study treatment. Subjects who participate in the study in compliance with the protocol for the 24 weeks of study drug administration, and complete the follow up period, will be considered to have completed the study.

For subjects who complete the study, or for those who withdraw prematurely from the study, final evaluations will be performed on the last day the subject receives the study drug, or as soon as possible afterwards. Subjects with ongoing AEs or clinically significant laboratory test abnormalities (as determined by the investigator) will be monitored as described in Section 8.1.3 and Section 8.1.2.4, respectively.

The following procedures will be performed at the end of study visit:

- E₂, LH and FSH concentrations (only if the subject's menses does not recover before Week 40)

- VAS assessment
- Vital signs
- Review of AEs
- New or changed concomitant medications/therapies
- Review of menses recovery status and record the date of menses onset (if applicable)

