The severity of endometriosis-associated pain will be assessed by the subject at Day 1 (baseline), Weeks 4, 8, 12, 16, 20, 24, and at the end of study visit using a 10 cm VAS. Subjects will be asked to assess their most severe endometriosis-associated pain over the preceding 4 weeks. For the Day 1 (baseline) assessment, if subjects had undergone endometriotic surgery within the previous 4 weeks, they will be asked to assess their most severe endometriosis-associated pain postsurgery. The VAS to be used is presented in Appendix 1.

7.3.3 *Recovery of Menses*

Status of menses recovery will be assessed at all study visits, including the follow-up period (Weeks 28, 32, 36 and at the end of study visit). The date of menses (if available) will be recorded at the end of study visit. Time to menses recovery will be defined as the time (in days) between the date of the last dose of study drug and the date of the first day that the subject observed menstrual bleeding of the next menses period. Any subjects withdrawing from the study without menstrual bleeding will be censored in this analysis at the date of withdrawal. Any subjects without menstrual bleeding prior to the end of study visit will be censored in this analysis at the date of the end of study visit.

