7.6.4 Exploratory Analysis

The analyses of exploratory efficacy endpoints (see Section 3.3) will be performed on the FAS subjects using as-randomised assignments.

Percentage of subjects castrated 1) $E_2 \leq 184$ pmol/L (50 pg/mL) 2) $E_2 \leq 110$ pmol/L (30 pg/mL) at Week 24:

The number and percentage of subjects castrated (according to each criterion) will be presented by treatment group at Week 24. The difference in percentage between the treatment groups and its 2-sided 95% CI will be presented and calculated using the same method as primary efficacy analysis.

Change in endometriosis-associated pelvic pain (by 10cm VAS) at Weeks 16, 20 and 24 and the end of study visit compared to baseline:

Endometriosis-associated pelvic pain measured by 10 cm VAS and change from baseline, will be summarised by treatment groups and overall at each time point, using summary statistics (n, mean, median, SD and minimum and maximum values) and the 95% CI for the true difference in mean VAS score and VAS change from baseline scores will be presented.

The 95% CI for difference in mean and change from baseline values are calculated using MMRM, same as those used in secondary analyses of VAS.

The mean and change from baseline of VAS at each time point are also analysed by subgroups of baseline VAS (VAS>3 cm, VAS≤3cm).

Serum E2, FSH and LH Concentrations at Week 24:

Serum E2, FSH and LH concentrations and change from baseline will be summarised at Week 24, using descriptive statistics (n, mean, median, SD and minimum and maximum values) and the 95% CI for the difference between treatment groups in mean concentration values and mean change from baseline values will be presented for each parameter.

The 95% CI for the difference in mean and change from baseline values are calculated using MMRM, same as those used in secondary analyses of VAS.

The PK/PD relationship will be explored (PD markers being E2, FSH and LH).

The data for subject individual plasma triptorelin concentration and PD markers in the each treatment groups will be combined to explore the relationships between PK concentrations and PD markers on the PK/PD relationships analysis set. PK/PD modelling will be described in a separate data analysis plan and reported in a standalone report.

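### The end of study pain comparison pools women seen just after menses return with women seen at Week 40 without it, so an arm gap in recovery can pass for a pain difference

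*Protocol*

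**What the plan says.** The endpoint, in the Protocol synopsis and again in section 3.2.4, is "Change in endometriosis-associated pelvic pain (by 10 cm VAS) at Weeks 16, 20 and 24 and the end of study visit compared to baseline".

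- **Visit timing.** Protocol 5.2.4.4: "The end of study visit will be the first visit within 15 days after the first day of menses recovery, or at Week 40", whichever comes first. Women who withdraw early also attend this visit.
- **Recall period.** Protocol 7.3.2: "Subjects will be asked to assess their most severe endometriosis-associated pain over the preceding 4 weeks". The VAS is among the procedures at the end of study visit.
- **Analysis.** Protocol 10.4.6.3 presents a 95% CI for the between-arm difference in mean VAS and in mean change at each time point, this visit included. SAP 7.6.4 says the intervals are "calculated using MMRM, same as those used in secondary analyses of VAS". The model in SAP 7.6.2 adjusts for treatment, its interaction with visit, and the stratification factors. Part of that text is blacked out; nothing visible refers to menses status. The additional subgroups are by surgical history or baseline VAS.
- **Visit assignment.** The text of SAP 6.1 re-maps early withdrawal visits to calendar windows. The column heading of SAP Table 1 also names end of study visits, and its last row (Week 40) starts at Day 278.
- **Menses and symptoms.** Protocol 1.1: "The suppression of menses is known to reduce endometriotic deposits and improve clinical symptoms". No figure in centimetres is given.

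**The concern.** The timing of the visit is set by an event after randomisation that is itself a secondary endpoint (time to menses recovery). That event also decides what the pain score measures. A recovered woman seen on time rates four weeks that include her first bleed. A woman seen at Week 40 without recovery rates four weeks with no bleed. Baseline VAS is taken on days 1 to 5 of menses (Protocol 5.2.2). The change from baseline therefore compares bleed with bleed for the first woman, and no bleed with bleed for the second. A pooled mean change mixes these two quantities even when recovery is the same in both arms.

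Between arms, the result depends partly on how many women in each arm have not recovered by Week 40. An arm with more of them could show lower pain for that reason alone, and this could be reported as lasting pain relief. No fixed-time VAS is scheduled between Week 24 and the end of study visit, so there is no other follow-up pain measure to set beside it.

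**Working it through.** **The plan's own figure.** The plan gives no precision for this endpoint. Its only sample size calculation is for the Week 12 non-inferiority test, and that reproduces. With 92% in both arms, a 10-point margin and one-sided 0.025, n = (1.960 + 1.036)² × 2 × 0.92 × 0.08 / 0.10² = 132.2, so 133 per arm, with power 85.2%. Allowing for 10% dropout, 133/0.9 gives 148 per arm, or 296 against 300 planned. The present point does not depend on this.

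**Does the window always contain the bleed?** The visit is at most 15 days after menses onset and recall is 28 days. As 15 < 28, yes, for every recovered woman seen on time.

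**Could recovery by Week 40 differ?** Scheduled last doses are Day 85 (3-month arm) and Day 141 (1-month arm) (Protocol 5.2.3). Day 281 is therefore 281 − 85 = 196 and 281 − 141 = 140 days after the last dose. The documents give no recovery rate for either arm, so neither the existence nor the direction of a gap is known.

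**Size.** Menses-driven difference = (gap in share unrecovered at Week 40) × (extra worst pain in a window with menses). Both inputs are assumed.

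| Gap in share unrecovered | 1 cm | 2 cm | 3 cm | 4 cm |
|---|---|---|---|---|
| 0 points | 0 | 0 | 0 | 0 |
| 5 points | 0.05 | 0.10 | 0.15 | 0.20 |
| 10 points | 0.10 | 0.20 | 0.30 | 0.40 |
| 20 points | 0.20 | 0.40 | 0.60 | 0.80 |

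**Against the precision.** With 150 × 0.9 = 135 per arm and an assumed SD of 2.5 cm, the half-width is 1.96 × 2.5 × √(2/135) = 0.60 cm. The chance that the 95% CI excludes zero, with no other pain difference, is:

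- 5% at 0 cm
- 10% at 0.20 cm
- 26% at 0.40 cm
- 75% at 0.80 cm

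**Slower recovery versus incomplete recovery.** A simulation used log-normal recovery times counted from Day 169 (log-SD 0.4) and 3 cm of extra pain with menses, all assumed.

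- Medians of 80 and 50 days leave 20% and 2% unrecovered at Week 40. The difference is −0.54 cm, favouring the slower arm.
- Medians of 40 and 25 days leave 0.5% and 0% unrecovered. The difference is −0.02 cm, although one arm is plainly slower.

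**If Table 1 re-maps completers.** A woman seen before Day 278 leaves the Week 40 row. She goes to the Week 28, 32 or 36 row, where no VAS is otherwise scheduled, or to Week 24, where her score is used only if no scheduled value exists. In the 80 v 50 day case, 28% and 4% of women stay in the Week 40 row, and 72% and 55% of those are unrecovered. The row is then a subset selected by late or absent recovery.

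**The case against.** - **Slower recovery alone does not produce the effect.** A reader might infer that whichever arm recovers more slowly will look better on pain. The documents do not support that. Among women who recover by Week 40, the visit is tied to the same event in both arms. What is needed is a gap in the share unrecovered at Week 40. This stands, and the point is limited accordingly.
- **The size rests on chosen inputs.** No recovery rate, VAS SD or menses-related pain difference is given. In the table, only a 20-point gap with 3 or 4 cm reaches the half-width. A reader might infer that the artefact will usually rival the interval; nothing in the documents shows that. This also stands.
- **The contrast is still randomised.** If a formulation leaves more women without menses and with less pain, that is a consequence of treatment and not a false number. This is fair, and the fault is one of interpretation. But the planned output is presented as a change in pain at a visit, alongside fixed visits, with nothing to show that it partly reflects menses status.
- **Readers can see the imbalance elsewhere.** SAP 7.6.2 reports recovery counts, censoring reasons and Kaplan-Meier curves. That helps, but it does not show pain by menses status.
- **Absence of menses is not proof of continued suppression.** The documents define only whether menses have returned; Week 40 hormones are listed, not analysed. It is safer to speak of women without menses recovery.

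**Conclusion.** The concern holds in a conditional form. The end of study VAS is collected at a visit triggered by menses, with a recall window that contains a bleed for recovered women seen on time and none for women unrecovered at Week 40. The plan still gives one between-arm interval. Depending on how Table 1 is read, that interval either pools over menses status or is computed on women selected by it.

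A misleading arm difference requires two things: a between-arm gap in the share unrecovered at Week 40, and more pain with menses. Protocol 1.1 makes the second plausible, but neither is quantified. Under the assumed ranges the effect runs from 0.05 to 0.80 cm; with no gap it is zero.

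The impact is confined to one visit of an exploratory endpoint analysed on the FAS, with no margin or formal test. The Week 12 primary result and the secondary VAS results to Week 12 are untouched.

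**What to change.** - **SAP 6.1:** state that completers' end of study VAS is not re-mapped to calendar visits, and make the Table 1 column heading agree with the text.
- **SAP 7.6.4, comparison:** keep Weeks 16, 20 and 24 in the MMRM comparison and take the end of study visit out. State that no between-arm conclusion on pain will be drawn from a pooled end of study value.
- **SAP 7.6.4, reporting:** summarise end of study VAS and change from baseline descriptively by arm in four rows: seen after recovery; seen at Week 40 without recovery; early withdrawal without recovery; menses never stopped. Give n, share of the arm, and days from last dose in each row.

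The cost is SAP wording and one split table, using menses status and dates already collected. The rows are defined after randomisation, so comparisons within a row are descriptive only. That is acceptable for an exploratory endpoint.
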